11.2 Sample Size/Accrual Rate

Because the number of patients enrolled at each dose level depends on observed toxicities, it is not possible to state a definite sample size that will be accrued. The dose escalation plan does allow for a minimum of 4 additional patients to be enrolled (if the first two patients enrolled experience dose-limiting toxicity as do patients at each of two CRM-defined de-escalated dose levels) and a maximum of 20 additional patients to be enrolled and treated. It is expected that the actual enrollment will fall well between these two extremes.

It is expected that this study will accrue approximately 10-12 patients per year.

11.3 Stratification Factors

This study will not stratify patients according to any baseline factors.

11.4 Analysis of Secondary Endpoints

11.4.1 Delineation of the local and systemic immune response to M032 administration.

- Virus reactivation and shedding will be detected by PCR and culture of serial serum and saliva samples.
- Immunogenicity of M032 will be evaluated by the use of ELISA to detect HSV antibody titers.
- Each of these binomial responses will be summarized by frequencies for each cohort and overall.

11.4.2 Gather preliminary information about the potential benefit of M032 in the treatment of patients with recurrent malignant gliomas.

- The percentage of patients experiencing complete response, partial response, stable disease and progressive disease will be reported by cohort and overall based on follow-up radiographic imaging.
- Changes in clinical disease status and steroid administration will be considered when reviewing changes in tumor volumetric size.
- All changes in tumor volume will also be analyzed with consideration of any other anti-tumor cancer therapies (either prior to M032 administration or following M032 failure) and the timeframes in which they were administered.

- Quality of life response: A Karnofsky Performance Status score will be recorded pre-treatment and then measured serially post-treatment for each patient. Time to KPS <60 will be measured for each patient by the Kaplan-Meier analytical method.

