- Disseminated HSV Infection: Disseminated multi-organ disease attributed to HSV is exceedingly uncommon, even in the immunocompromised host. Such disease has been encountered in the newborn with disease identified as 'disseminated multiorgan involvement' and occurs in about 25% of newborns with this disease (incidence 1:10,000 deliveries).[38] In adults, disseminated disease has been encountered in stem cell transplant recipients and, very rarely, pregnant women.[39] In all circumstances, disseminated disease is associated with a systemic host response of fever, and findings compatible with sepsis, including hepatic dysfunction. To monitor for these rare events, most importantly, serial physical examinations will be performed to assess for fever and symptoms of sepsis or hepatic dysfunction. In addition, serial blood specimens will be obtained at Days 2, 10, 28 and monthly thereafter and cultured for infectious HSV. Any positive cultures will be analyzed by PCR to discriminate between wild type HSV-1 and mutant M032 HSV. Should a patient develop fever, rash, or unexplained elevations in liver function tests in conjunction with a concomitant increase of infectious HSV by plaque assay in blood specimens (exceeding prior values by 2 logs), patients will undergo a 21 day course of treatment with acyclovir for presumed disseminated HSV infection. Parenthetically, it should be noted that oncolytic HSV therapy for metastatic colon carcinoma involving the liver led to detectable HSV DNA in the blood but in the ABSENCE of clinical symptomatology[40]; thus, increasing levels as well as fever will both be required to therapeutically intervene. Should 2 Grade 3 or 4 toxicities attributable to disseminated HSV infection occur in the same dose level, the prior dose level shall be declared the MTD and enrollment will be halted.

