7. CORRELATIVE/SPECIAL STUDIES

To address secondary objectives of the protocol, additional correlative studies will be performed on blood/serum, conjunctival secretions, saliva samples and tumor tissue samples.

Blood Samples: Blood samples (heparinized) will be taken at Baseline, on Days 0, 2, 3, 10, 28 and at Months 3, 6, 9 and 12. One ml of each sample will be submitted to the Clinical Virology Diagnostic Laboratory for HSV culture to determine the amount of virus shedding. The balance of the blood sample will be separated by density gradient centrifugation to provide plasma (serum) and peripheral blood mononuclear cells (PBML). Plasma will be tested to permit detection and quantification of HSV antibody titer pre-and post-inoculation via ELISA. Peripheral blood mononuclear leukocytes will be quantified for subsets and other leukocyte markers by FACS analysis, expression of activation signals (intracellular lymphocyte interferon-gamma levels) and lymphocyte transformation assays will also be performed to assess aspects of the T_H1 response to treatment with M032. Plasma cytokine assays will be performed to quantify changes over time from baseline. Conjunctival, blood and saliva will be assessed for HSV shedding by standard culture methods. Any positive cultures will be further

characterized for wild-type or M032 HSV by PCR. Any remnant blood will be stored for future brain tumor research.

Tissue Samples: If available, remnant brain tissue from the biopsy will be snap-frozen in liquid nitrogen and stored for future research. Should any patient with recurrent tumor after HSV treatment be determined to benefit from additional tumor resection for diagnosis or to ameliorate intractable symptoms caused by increased mass effect and intracranial edema, the tumor will be removed *en bloc* as much as possible and sectioned in 2-4mm thick slices perpendicular to the placement of the catheters. Each section will be cut into quarters and each quarter will be labeled 1, 2, 3 or 4, processed and stored for future research as follows:

Quarter 1: Snap freeze in liquid nitrogen for immediate assessment of viral replication *in vitro*.

Quarter 2: Snap freeze in liquid nitrogen for RNA and DNA extraction and the following evaluations:

- Quantitative PCR (vector replication *in-vivo*; compare number of copies to vector input)
- RT-PCR to detect HSV polymerase mRNA (vector replication *in-vivo*)

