8. STUDY CALENDAR

	Pre-Study (within 2 weeks prior to the administration of M032)	Day 0	Day1	Day 2	Day 3	Day 10 (± 3 days)	Day 28 (± 4 days)	Month 2 (± 12 days)	Month 3 (± 12 days)	Months 4, 5 (± 12 days)	Months 6, 9, 12 (± 12 days)	Unscheduled ²⁰
Informed consent	X ¹											
Inclusion/ Exclusion Criteria	X											
Demographics	X											
Pregnancy test-serum ⁴	X											
Medical history	X											
Concurrent meds	X	X	X	X	X	X	X	X	X	X	X	X
Complete physical exam (including wound assessment Days 1-10)	X		X	X ¹⁷	X ¹⁷	X	X		X		X	X ²¹
Vital signs	X	X	X ²	X ²	X ²	X	X		X		X	X ²¹
KPS	X				X	X	X		X		X	X ²¹
CBC w/diff, plts	X			X		X	X	X	X	X	X	X
Serum chemistry ³ , PT/INR, PTT	X			X		X	X	X	X	X	X	X
HIV serology	X											
EKG	X											
CXR (AP and lateral)	X											
Urinalysis with micro	X											
Adverse event evaluation ^{11, 12}		X	X	X	X	X	X	X	X	X	X	X
MRI ⁵	X ¹³	X			X		X		X		X	X ²¹
Neurologic exam	X	X	X ⁶	X ⁶	X ⁶	X	X		X		X	X ²¹
HSV Ab titer ⁷	X					X	X		X		X	X
HSV detection (saliva, conjunctival secretions, blood) ⁸	X			X ¹⁸	X ¹⁸ blood only	X	X	X	X	X	X	X
IL-12 detection (serum) ⁹	X			X ¹⁸	X ¹⁸	X	X		X		X	X
Blood sample for LTA, Elispot	X			X ¹⁸	X ¹⁸	X	X		X		X	X
IFN gamma assay	X			X ¹⁸	X ¹⁸	X	X		X		X	X
Blood to be stored for future immune studies	X	X ¹⁵		X ¹⁸	X ¹⁸	X	X		X		X	X
Head CT		X ¹⁰										

	Pre-Study (within 2 weeks prior to the administration of M032)	Day 0	Day 1	Day 2	Day 3	Day 10 (± 3 days)	Day 28 (± 4 days)	Month 2 (± 12 days)	Month 3 (± 12 days)	Months 4, 5 (± 12 days)	Months 6, 9, 12 (± 12 days)	Unscheduled ²⁰
Biopsy, Catheter placement		X										
Prophylactic AED	X	X	X	X	X	X	X ¹⁶					
M032 Administration			X									
Rickham/Ommaya reservoir aspiration ¹⁹	X	X	X	X	X	X	X		X		X	X ²¹

1. Will be obtained prior to study screening procedures.
2. Frequency post initiation of infusion: vital signs will be every hour for 12 hours post initiation, every 2 hours for the next 12 hours, then every 4 hours for the next 24 hours.
3. Includes sodium, potassium, chloride, bicarbonate, glucose, BUN, creatinine, calcium, phosphorus, total protein, uric acid, GGT, AST/ALT, CK, LDH, alkaline phosphatase, total bilirubin, cholesterol, triglyceride.
4. Only women of child-bearing potential. If necessary, can be repeated during the course of the study.
5. All MRI scans will be performed as prescribed by the Principal Investigator.

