6. Neurological exam includes assessment of cranial nerve abnormalities, gait abnormalities (when appropriate), sensory abnormalities, muscle strength, and level of consciousness. This will be evaluated every hour for 12 hours post initiation, every 2 hours for the next 12 hours, then every 4 hours for the next 24 hours.
7. By ELISA; neutralizing antibody assays may also be performed.
8. Samples will be evaluated by PCR and culture; quantitative PCR may be performed on positive samples.
9. IL-12 detection (serum) by ELISA.
10. After catheter placement but before start of infusion; may also take place on Day 1.
11. All AEs will be assessed throughout the course of the study, but specific CRFs will only be required at the time points delineated in the above schedule.
12. All unresolved toxicities be followed regularly by the treating physician and/or research coordinator; the nurse coordinator will conduct follow-up weekly with the subject, family and/or referring physician (by phone if travel is too burdensome for the subject) until resolution of treatment-related toxicity to less than Grade 2 (or Grade 3 if that was the subject's baseline).
13. MRI's that have been obtained within 30 days of pre-study visit may be used at the discretion of the PI.
14. Sample will be stored for future brain tumor research.
15. To be obtained post-op.
16. Prophylactic AED's may be discontinued at the Day 28 visit.
17. Wound examination only.
18. Acceptable up to 2 days after
19. Should a patient have an access device (eg., Rickham or Ommaya reservoir) that accesses either the more central portion of the tumor/cyst, or the CSF space, fluid will be aspirated as possible (expected, 2-10cc) from the catheter for laboratory studies. These specimens will be obtained at either the pre op clinic visit or the day of surgery, as well as up to daily during the inpatient hospitalization (per the surgeon's discretion), and again at post op visit day 10, Day 28, and Months 3,6,9 and 12.
20. If a participant is to miss a regularly scheduled research follow-up visit, an unscheduled visit can be conducted to capture research data at an otherwise standard of care clinic visit.
21. Collected only if done during an otherwise non-research visit (i.e., unscheduled visit).

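### The shedding analysis in Section 11.4.1 omits conjunctival secretions and names serum instead of blood, and the sections disagree on whether PCR detects virus or types positive cultures

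*Combined protocol and SAP*

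**What the plan says.** **Analysis rule.** Section 11.4.1 says "Virus reactivation and shedding will be detected by PCR and culture of serial serum and saliva samples", and closes with "Each of these binomial responses will be summarized by frequencies for each cohort and overall". It gives no rule for combining specimens, assays or visits into one yes/no result per patient.

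**Specimens collected.** Section 7 says "Conjunctival, blood and saliva will be assessed for HSV shedding by standard culture methods". The calendar row in Section 8 reads "HSV detection (saliva, conjunctival secretions, blood", and the visit lists in Section 8.1 collect conjunctival secretions together with saliva. For blood, Section 7 says "One ml of each sample will be submitted to the Clinical Virology Diagnostic Laboratory for HSV culture to determine the amount of virus shedding". Only the balance of that heparinized sample is then separated into plasma and cells.

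**Assay.** Two places describe culture followed by PCR typing. In Section 7, positive cultures are to be further "characterized for wild-type or M032 HSV by PCR". Section 5.1, on disseminated infection, says "Any positive cultures will be analyzed by PCR to discriminate between wild type HSV-1 and mutant M032 HSV". Two other places use both assays for detection: Section 11.4.1, and calendar footnote 8, which says "Samples will be evaluated by PCR and culture; quantitative PCR may be performed on positive samples".

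**The concern.** A statistician programming the shedding table from Section 11.4.1 would take saliva and serum results and have no instruction to use the conjunctival ones. A patient positive only at the conjunctiva could then be missing from the shedding count even though the sample was collected and assayed. It is also unclear which blood result enters the table.

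The assay wording adds a second ambiguity. A sample that is PCR-positive and culture-negative is a positive under Section 11.4.1 and footnote 8. Under the sequence in Sections 7 and 5.1 it would not be found.

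The synopsis lists shedding of M032 among the safety evaluations, and the agent is a virus able to replicate in tumor cells. The reported frequency should not depend on which section the laboratory or the programmer happened to follow. With at most 24 patients, reclassifying one or two of them visibly changes a cohort's percentage.

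**Working it through.** The documents state no expected shedding rate, test or sample size for this endpoint, so there is no planned figure to reproduce. The check compares the texts and counts specimens.

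**1. Texts side by side**

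| Place | Specimens | Role of PCR |
|---|---|---|
| 11.4.1 (analysis) | serum, saliva | detection, alongside culture |
| 7 (correlative studies) | conjunctival, blood, saliva | typing of positive cultures |
| 8, calendar row and footnote 8 | saliva, conjunctival, blood | detection, alongside culture; quantitative PCR optional on positives |
| 5.1 (disseminated HSV) | blood | typing of positive cultures |

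Section 11.4.1 stands alone on specimens. On assay, the four places split two and two.

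**2. Scheduled post-treatment specimens per patient** (Section 8 calendar, HSV detection row; unscheduled visits not counted)

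- Blood: Days 2, 3, 10, 28 and Months 2, 3, 4, 5, 6, 9, 12 = 11.
- Saliva: the same visits without Day 3, which is blood only = 10.
- Conjunctival: as saliva = 10.
- Total: 11 + 10 + 10 = 31.
- Not named in 11.4.1: 10/31 = 32%. This takes serum as standing for the blood specimen, so 21 of 31 are covered.

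**3. Direction.** Count a patient as positive if any sample is positive. Every patient who is positive on two sites is also positive on three. Every patient who is positive by culture is also positive under a rule that accepts culture or PCR. The narrower count is therefore at most equal to the wider one. This concerns HSV of any type; separating M032 from wild-type virus is a distinct question, taken up in the fix.

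**4. Size: illustration only.** Assume that each site is PCR-detectably positive in a proportion p of patients, independently across sites, with 24 patients. The probability of any positive is 1 − (1 − p)^k for k sites.

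| Assumed p | Three sites | Two sites | Expected patients, three vs two sites |
|---|---|---|---|
| 0.05 | 14.3% | 9.8% | 3.4 vs 2.3 |
| 0.10 | 27.1% | 19.0% | 6.5 vs 4.6 |
| 0.20 | 48.8% | 36.0% | 11.7 vs 8.6 |

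If nobody is positive only at the conjunctiva, omitting that site loses nothing.

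For the culture step, let s be the assumed sensitivity of culture relative to PCR, so that the three-site figure is 1 − (1 − ps)^3. With p = 0.10 this gives 27.1% at s = 1 (no loss), 14.3% at s = 0.5 and 8.7% at s = 0.3. Neither p nor s is given in the documents.

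**The case against.** A reader might infer that shedding will be undercounted, by about 30%. The documents do not support that. A loss needs patients who are positive only at the conjunctiva, or PCR-positive and culture-negative, and it needs staff to follow the narrower text. The 30% comes from assumed, independent rates: for small p it does little more than restate that one site in three is missing. Positive correlation between sites would shrink it.

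A reader might also infer that blood is left out, or that culture-gated PCR is the settled plan. Neither holds. Serum comes from blood, so this is a mismatch of specimen and not an omission. Section 11.4.1 itself already specifies PCR and culture. Section 7 describes PCR as a typing step but does not expressly exclude PCR for detection.

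The importance is limited too. Shedding is summarized descriptively. It does not enter the dose-limiting toxicity definition, the continual reassessment model or the halting rules. The contact and contraception periods in Section 3.1.8 are fixed and are not tied to the observed frequency. Monitoring for disseminated infection is specified separately in Section 5.1.

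These points limit the size and the consequence. What stands is that the only analysis rule does not name a site the trial samples at ten scheduled post-treatment visits, and that the assay texts differ.

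**Conclusion.** The point holds as an inconsistency with a known direction and an unknown size. Section 11.4.1 does not name 10 of the 31 scheduled post-treatment HSV-detection specimens per patient, says serum where Section 7 cultures blood, and treats PCR differently from Sections 7 and 5.1. If the narrower text is followed, the any-site shedding frequency can be too low and cannot be too high. That statement assumes the serum and blood results refer to the same specimen and that a patient counts as positive on any positive sample. The shortfall, which may be zero, cannot be computed from the documents. The primary endpoint and dose finding are unaffected. The correction is still worth making because shedding is a listed safety evaluation and the samples and both assays are already planned.

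**What to change.** In Section 11.4.1:

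- List the specimens as saliva, conjunctival secretions and blood.
- Define a shedding-positive patient as one with any post-treatment sample positive, at any site, by either assay.
- Report M032 and wild-type HSV separately. Without this, an any-positive rule would mix reactivated wild-type virus with shedding of the study agent.
- Show baseline positives separately, since the calendar also schedules HSV detection before treatment.
- Tabulate by site, visit and assay, so that culture and PCR results stay distinguishable.

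Then reconcile the detection-assay wording in Sections 5.1 and 7 with footnote 8 and Section 11.4.1, which already plan PCR and culture. PCR typing of positive cultures can remain as an additional step. This concerns detection wording only and does not touch the treatment criteria in Section 5.1.

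The cost is a wording amendment and slightly more tabulation. No new samples are needed and no assay is added beyond those in footnote 8. The reported shedding frequency may come out higher.

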APPENDIX A

Expected Adverse Events Associated with M032 and Related International Medical Terminology (IMT) Terms

Category	Adverse Event	IMT Preferred Term
Allergy/Immunology	Allergic reaction/hypersensitivity	Hypersensitivity NOS
Blood/Bone Marrow	Leukocytes	Leucopenia NOS
Blood/Bone Marrow	Hemoglobin	Haemoglobin decreased
Blood/Bone Marrow	Hemolysis	Hemolysis NOS
Cardiovascular (General)	Edema	Oedema NOS
Cardiovascular (General)	Thrombosis/embolism	Thrombosis NOS
Constitutional Symptoms	Fatigue	Fatigue
Constitutional Symptoms	Fever	Pyrexia
Constitutional Symptoms	Weight loss	Weight decreased
Gastrointestinal	Nausea	Nausea
Hemorrhage	Hemorrhage/bleeding without grade 3 or 4 thrombocytopenia	Haemorrhage NOS
Hepatic	SGPT (ALT)	Alanine aminotransferase increased
Infection/Febrile Neutropenia	Infection without neutropenia	Infection NOS
Neurology	Pyramidal tract dysfunction	Upper motor neurone lesion
Neurology	Speech impairment	Speech disorder NEC
Neurology	Memory loss	Amnesia NEC
Neurology	Confusion	Confusion
Neurology	Mood alteration—depression	Depression NEC
Neurology	Personality/Behavioral	Personality change
Neurology	Neurology—Other (Specify, Somnolence)	Not Available
Neurology	Depressed level of consciousness	Depressed level of consciousness
Neurology	Seizure(s)	Convulsions NOS
Neurology	Neurology—Other (Specify, Tumor Progression)	Not Available
Pain	Headache	Headache NOS

Note: The full list of IMT terms is available on the CTEP home page (<http://ctep.info.nih.gov/CtepInformatics/IMT.htm>).

APPENDIX B

Performance Status Criteria

Karnofsky Performance Scale	
Percent	Description
100	Normal, no complaints, no evidence of disease.
90	Able to carry on normal activity; minor signs or symptoms of disease.
80	Normal activity with effort; some signs or symptoms of disease.
70	Cares for self, unable to carry on normal activity or to do active work.
60	Requires occasional assistance, but is able to care for most of his/her needs.
50	Requires considerable assistance and frequent medical care.
40	Disabled, requires special care and assistance.
30	Severely disabled, hospitalization indicated. Death not imminent.
20	Very sick, hospitalization indicated. Death not imminent.
10	Moribund, fatal processes progressing rapidly.
0	Dead.

APPENDIX C**INSTRUCTION FOR M032 DOSE PREPARATION****Preparation of M032 dilutions will take place in the hospital pharmacy.**

M032 (NSC 733972) should be prepared for administration following Biosafety Level 2 Guidelines using a laminar flow biological safety cabinet, hood, gloves, safety glasses and gown.

MATERIALS NEEDED FOR PREPARATION OF M032 DOSE FOR SUBJECT ADMINISTRATION

1. 70% Isopropanol solution
2. MetriSpray, Cavicide or equivalent disinfectant.
3. 5 cc Becton-Dickson disposable syringes, Product code (total of 4 syringes needed)
4. Tuberculin syringe and 18-23 G needle
5. Sterile Vector Diluent (10% Glycerol in Phosphate Buffered Saline, pH 7.0-7.4, USP, preservative-free for injection, 50 cc bottles, Alanza, Inc.) cooled to 4°C.
6. Sterile Gloves
7. Alcohol Swabs/Wipes
8. Kim-wipes

EQUIPMENT NEEDED FOR PREPARATION OF M032 DOSE FOR SUBJECT ADMINISTRATION

1. Laminar Flow Biological Safety Cabinet (LFBSC)
2. Rack for vector M032 Stock Vials
3. Refrigerator
4. Wet ice or coolant

METHOD FOR PREPARATION OF M032 DILUTION FOR SUBJECT ADMINISTRATION

1. Remove all items from the LFBSC, wipe down work surfaces with MetriSpray, Cavicide or equivalent disinfectant, followed by 70% isopropanol, allow blower to run for 15 minutes prior to using.
2. Cool virus diluent (sterile preservative-free 10% Glycerol in Phosphate Buffered Saline, pH 7.0-7.4, USP) to approximately 4°C in a refrigerator or on ice.
3. Thaw the appropriate number of vector stock M032 vial(s) according to Table 1 in **Appendix D Dose Preparation Guide** below, by rubbing gently between gloved hands. Continue until the last ice crystals have melted and then place vials on ice.
4. Note the time that the contents have completely thawed. Do not allow the vials to warm.
5. Wipe stock M032 vials dry with Kim-Wipes. Gently mix contents of stock M032 vials by swirling.
6. Wipe stock M032 vials with alcohol swab and place in a vial rack in the LFBSC to dry.
7. Dilute M032 according to Table 1. Dose Preparation Guide
 - 7.1 Draw up the required amount of sterile preservative-free Phosphate-buffered saline + 10% glycerol (Alanza), USP for injection (vector diluent)
 - 7.2 Remove the required volume of stock M032 from the glass vials. Add stock M032 to the receptacle/vehicle containing the required diluent
 - 7.3 Gently invert end over end at least 5 times to mix contents

